15.2 Demographic and Baseline Characteristics

The following demographic variables at screening will be summarized: race, age, height and weight.

153 Analysis of Primary Endpoint

McNemar's tests will be performed to evaluate whether there is a statistically significant difference in nausea response (dichotomously scored as present or absent) across the test product (intranasal naloxone) and control product (intranasal placebo) conditions.

154 Analysis of Secondary Endpoints

Linear mixed effects regression modeling will be performed to assess differences across conditions in rate of cortisol change over the course of all assessments (baseline and 20 and 50 minutes post-administration).

155 Sample Size and Randomization

We do not expect any nausea responses to the control product. Under the null hypothesis of no difference between conditions, we would also expect no nausea responses under the alternative. In terms of probability, "no responses" implies a probability of 0: In other words, an impossible event. A single nausea response to intranasal naloxone would decisively refute the null. But nausea responses, under either condition, are not literally impossible. We have therefore powered against the expected value of 0 by using the beta distribution with $r = 0$ as a Bayesian prior, in place of the usual point value. The beta with $r = 0$ is a U-shaped distribution concentrating most of the density on the extreme values. Specifically, for values of p from .01 to .99, in .01 increments, we calculated the ordinate of the beta distribution with trial values of N ; calculated the one-tailed rejection region (outcomes of fewer than 0 nausea responses were not considered) for that value of p and N ; calculated the power for that N and an alternative value of p (e.g., .4); then used the corresponding ordinate for each value of p as a weight, and calculated the average across the range from .01 to .99 as our estimate of power. Since nausea responses are not literally impossible, we also explored power with null proportions up to .3, with the alternatives in the below table. For these nonzero values, a standard binomial power analysis would have sufficed, but for consistency we have used the corresponding Bayesian priors. The beta prior with $r = N/10$, for example, will concentrate probability on values near .1, whereas that with $r = 0$ will concentrate it around 0. The latter, approximating the impossible event, of course yields high power, whereas power declines as the binomial becomes more symmetrical. For the values of potential interest to us, an N of 24 will suffice for 80%+ power. (Following from the above rationale, the entries in the table below do not correspond to standard power calculations for the McNemar test. The test for 0% vs. 40%, for example, is a test of whether the percentages for the two populations are both 20%; the power of this test is just 1 of 99 values averaged, with weights from the beta distribution, for the results in the table below).

% Endorsing Nausea		Number Needed (N)	Power to detect difference
Control Product	Test Product		
0%	20%	20	.811
0%	30%	12	.823
0%	40%	9	.844
10%	40%	16	.817

20%	50%	21	.805
30%	60%	24	.805

Reference: Uebersax, J.S. Bayesian unconditional power analysis (2007).

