HIPAA	Health Insurance Portability and Accountability Act of 1996
ICF	Informed Consent Form
ICH	International Conference on Harmonisation
IEC	Independent Ethics Committee
IRB	Institutional Review Board
IM	Intramuscular
IN	Intranasal
IT	Information Technology
IUD	Intrauterine Device
IV	Intravenous
MAD	Mucosal Atomization Device
OS	Operating System
PI	Principal Investigator
SAE	Serious adverse experience
SID	Subject Identification Number
SC	Subcutaneous
SQL	Structured Query Language
SSL	Secure socket layer
UCSF	University of California – San Francisco
VPN	Virtual private network

PROTOCOL SYNOPSIS

TITLE	OPIATE WITHDRAWAL RESPONSES TO INTRANASAL NALOXONE AS AN INDEX OF ALTERED ENDOGENOUS OPIOID ACTIVITY AMONG WOMEN WITH OBESITY: A FEASIBILITY AND EFFICACY STUDY
SPONSOR	[name]
FUNDING ORGANIZATION	National Heart Blood and Lung Institute (NHLBI)
NUMBER OF SITES	1
RATIONALE	Understanding what drives compulsive overeating among individuals with obesity will lead to the development of more effective treatments. A large body of literature implicates the endogenous opioid system in eating behavior. Researchers have published the use of exogenous opioidergic blockade as a method to assess endogenous opioid activity in obesity ^{1,2} . Data suggest that women are more sensitive to exogenous opioidergic blockade. Our work shows that withdrawal responses, as indexed by nausea following opioidergic antagonism using oral naltrexone, are associated with non-homeostatic eating in obese women ^{1,2} . To (1) reduce the amount of time needed to investigate associations between eating behavior, obesity, and the endogenous opioid system, thereby reducing subject burden, and (2) take the initial steps toward the development of a cost-and time-effective method to assess endogenous opioid activity in women, we plan to evaluate the use of naloxone hydrochloride administered intranasally (intranasal naloxone).
STUDY DESIGN	This is a single-center, double-blind, placebo-controlled, randomized, crossover trial design.
PRIMARY OBJECTIVE	1. To determine if 2 mg/2 mL intranasal naloxone elicits the withdrawal symptom of nausea (present versus absent) in obese women.
SECONDARY OBJECTIVES	1. To determine if 2 mg/2 mL intranasal naloxone elicits other withdrawal symptoms, as measured by subjective opiate withdrawal scales ³ in obese women 2. To determine the rate of the cortisol response following 2 mg/2 mL intranasal naloxone in obese women
NUMBER OF SUBJECTS	24 women

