DURATION OF SUBJECT PARTICIPATION AND DURATION OF STUDY	Subjects will be in the study for up to 3 weeks. There will be a period of at least 24 hours between visits 1 and 2. Web-based eligibility: Screening for self-report eligibility criteria, approx. 15 minutes Phone Screen: Phone call to review eligibility and schedule visit 1, planning for visit 1, approx. 15 minutes Visit 1: In-person baseline assessment (screening for pregnancy and

	drug use), approx. & Administration day 1 (approximately 1.5-2 hours) Visit 2: Administration day 2 (approximately 1.5-2 hours) Recruitment and participation are expected to take 6 months
CONCOMITANT MEDICATIONS	
Allowed:
 
 1. Medications are permitted with use of naloxone hydrochloride unless listed below under “prohibited” 
Prohibited:
 
 1. Current use of opiate-containing medications 2. Current use of vasoconstrictor medication 3. Initiation of new medications that are contraindicated with naloxone hydrochloride use during the study period 4. Current use of insulin
EFFICACY EVALUATIONS	
 1. Self-reported nausea at 0 minutes (pre-administration), and 10 and 30 minutes following administration of test product or control product 2. Self-reported symptoms of withdrawal as measured by the subjective opiate withdrawal scale (SOWS³) at 0 minutes (pre-administration), and 10 and 30 minutes following administration of test product or control product 3. Salivary cortisol values at 0 minutes (pre-administration) and 20 and 50 minutes following administration of test product or control product
PRIMARY ENDPOINT	
 1. Presence or absence of the self-reported withdrawal symptom of nausea following administration of the test versus control product.
SECONDARY ENDPOINTS	
 1. Scores on self-report Subjective Opiate Withdrawal Scale (SOWS)³ following administration of the test versus control product. 2. Rate of the cortisol response, as measured by salivary cortisol, following administration of the test versus control product.
OTHER EVALUATIONS	N/A
SAFETY EVALUATIONS	Incidence of unexpected adverse events. Subjects will be monitored for unexpected adverse events and serious adverse events following administration of the test product and control product.

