1.2 Overview of Clinical Studies

From Package Insert: Pharmacokinetics: Distribution, Metabolism, and Elimination

Following parenteral administration, naloxone is distributed in the body and readily crosses the placenta. Plasma protein binding occurs but is relatively weak. Plasma albumin is the major binding constituent, but significant binding of naloxone also occurs to plasma constituents other than albumin. It is not known whether naloxone is excreted into human milk. Naloxone hydrochloride is metabolized in the liver, primarily by glucuronide conjugation with naloxone-3-glucuronide as the major metabolite. In one study the serum half-life in adults ranged from 30 to 81 minutes (mean 64 ± 12 minutes). In a neonatal study the mean plasma half-life was observed to be 3.1 ± 0.5 hours. After an oral or intravenous dose, about 25-40% of the drug is excreted as metabolites in urine within 6 hours, about 50% in 24 hours, and 60-70% in 72 hours.

[figure not shown]
From Package Inserts: Clinical Pharmacology

Naloxone hydrochloride prevents or reverses the effects of opioids including respiratory depression, sedation, and hypotension. It can also reverse the psychotomimetic and dysphoric effects of agonist-antagonists such as pentazocine. Naloxone hydrochloride is an essentially pure opioid antagonist, i.e., it does not possess the “agonistic” or morphine-like properties characteristic of other opioid antagonists. When administered in usual doses and in the absence of opioids or agonistic effects of other opioid antagonists, it exhibits essentially no pharmacologic activity. Naloxone hydrochloride has not been shown to produce tolerance or cause physical or psychological dependence. In the presence of physical dependence on opioids, naloxone hydrochloride will produce withdrawal symptoms. However, in the presence of opioid dependence, opiate withdrawal symptoms may appear within minutes of naloxone hydrochloride administration and subside in about 2 hours. The severity and duration of the withdrawal syndrome are related to the dose of naloxone hydrochloride and to the degree and type of opioid dependence.

From Published Research: Route of Administration

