3.2 Secondary Objectives

1. To determine if 2 mg/2 mL intranasal naloxone (1 mg/1 mL per nostril) elicits other withdrawal symptoms, as measured by subjective opiate withdrawal scales³ in obese women (compared to intranasal placebo).
2. To determine the rate of the salivary cortisol response following intranasal naloxone administration in obese women (compared to intranasal placebo).

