5.2 Secondary Efficacy Endpoints

1. Scores on self-report Subjective Opiate Withdrawal Scale (SOWS)³ following administration of the test versus control products. A complete score that captures the full range of withdrawal responses may reveal a withdrawal syndrome that occurs, in addition to, or in the absence of, nausea.
2. Rate of the cortisol response following administration of the test versus control products as measured by salivary cortisol. Cortisol increases following opioidergic blockade may index the degree to which an individual's opioid system controls the hypothalamic-pituitary-adrenal (HPA) axis, which is responsible for physiologic stress responses.

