8 STUDY TEST AND CONTROL PRODUCTS

8.1 Method of Assigning Subjects to Treatment Groups

Twenty-four eligible subjects will be randomly assigned to receive the test product (intranasal naloxone) or control product (intranasal placebo) first (on visit 1 versus on visit 2) in a 1:1 ratio using a SAS-based computer-generated randomization table computed by [name], of the UCSF Research Pharmacy Staff.

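### Must section 15.4 fix the form of time in the cortisol model, given that a linear slope over 0, 20 and 50 minutes hardly uses the 20-minute sample?

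*Combined protocol and SAP*

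**What the plan says.** The cortisol analysis is the single sentence in section 15.4. It specifies linear mixed effects regression to assess "differences across conditions in rate of cortisol change over the course of all assessments (baseline and 20 and 50 minutes post-administration". All three samples enter the model. The form of time, the covariance, a period term and the tested contrast are not stated there or elsewhere.

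The target is worded the same way throughout:
- Synopsis, secondary objectives: "To determine the rate of the cortisol response following 2 mg/2 mL intranasal naloxone in obese women".
- Synopsis, secondary endpoints: "Rate of the cortisol response, as measured by salivary cortisol, following administration of the test versus control product".
- Section 3.2: "To determine the rate of the salivary cortisol response following intranasal naloxone administration in obese women".
- Section 5.2: "Rate of the cortisol response following administration of the test versus control products as measured by salivary cortisol".

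Section 5.2 adds the rationale: "Cortisol increases following opioidergic blockade may index the degree to which" the opioid system controls the HPA axis. The order of the two products is randomised, naloxone or placebo "first (on visit 1 versus on visit 2) in a 1:1 ratio" (section 8.1).

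No cortisol time course, variance or expected effect appears anywhere. The sample size argument in section 15.5 concerns nausea only.

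**The concern.** Three unequally spaced samples are few for a slope. The mean time is 23.3 minutes, so the 20-minute sample sits close to the pivot of the fitted line and has almost no leverage. If rate means the condition-by-linear-time coefficient, one of the three samples is nearly wasted. A naloxone effect that peaks near 20 minutes and fades by 50 could then give a slope near zero, or slightly negative, although section 5.2 rests the endpoint on a cortisol increase.

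This is also the only analysis offered for the second secondary objective. With the form of time unstated, the choice could in principle be made after the data are seen. At stake are a missed response and some room for selective modelling on a secondary endpoint.

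**Working it through.** The plan states no cortisol figure, so there is none to reproduce.

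**Slope weights.** Inputs are the sampling times in section 15.4: t = 0, 20, 50.

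Mean t = 70/3 = 23.33. Sum of squares = 23.33² + 3.33² + 26.67² = 1266.67. Weight = (t - 23.33)/1266.67:

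| Time (min) | Weight per minute | Share of absolute weight |
|---|---|---|
| 0 | -.0184 | 43.75% |
| 20 | -.0026 | 6.25% |
| 50 | +.0211 | 50% |

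The 20-minute weight is -1/8 of the 50-minute weight. With independent errors the slope correlates sqrt(1250/1266.67) = .993 with the plain 50-minus-0 change.

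These weights hold under random intercepts, with or without a random slope, when each condition has its own baseline. They are not universal. A model with a common baseline and no subject-by-visit variation gives +.0069 at 20 minutes and +.0172 at 50 minutes, so the 20-minute sample has 29% of the weight. That falls to +.0015 when subject-by-visit variance equals residual variance, and to -.0011 at four times that.

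**What the slope sees.** For an effect D at 20 minutes and fD at 50 minutes, the fitted 50-minute change is 50 x (-.00263 + .02105f) x D:
- f = 1: .92D
- f = .5: .39D
- f = 1/8: 0
- f = 0: -.13D

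**Slope against a 2-df condition-by-time test.** Everything here is assumed except the 24 subjects and the times: complete pairs, SD 1 per sample, independent errors, two-sided .05, period x time fitted. Let a and b be the effects at 20 and 50 minutes.
- Slope: SE = sqrt(2 x .000789/24) = .00811, where .000789 = 1/1266.67. Noncentrality = (-.00263a + .02105b)/.00811.
- Joint test on the two changes from baseline: noncentrality = 8(a² - ab + b²).

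Each range runs from the paired form (t 22; F 2,21) to the random-intercept form (t 93; F 2,90).

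| Profile (a, b) | Slope noncentrality | Joint noncentrality | Slope power | Joint power |
|---|---|---|---|---|
| Gone by 50 min (1, 0) | -0.32 | 8.00 | .06 | .65-.70 |
| Half left (1, .5) | 0.97 | 6.00 | .15-.16 | .52-.57 |
| Sustained (1, 1) | 2.27 | 8.00 | .58-.61 | .65-.70 |
| Linear rise (.4, 1) | 2.47 | 6.08 | .65-.68 | .53-.57 |

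With serial correlation .5 per 30 minutes (paired form), slope against joint is .07 and .99, .20 and .94, .74 and .94, and .81 and .69 in the same order.

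The slope is the better test once the 50-minute effect exceeds the 20-minute effect by a factor of 1.16 (paired) to 1.24 (random intercept) with independent errors, or 1.55 (paired) at correlation .5.

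At 0.5 SD with independent errors, both tests are weak: .19-.20 against .20-.22 (sustained), .08 against .16-.17 (half left), .22-.23 against .16-.18 (linear rise).

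**Which profile do the documents support?** None directly. Section 1.2 gives a mean serum half-life of 64 minutes. It also says that in opioid dependence "opiate withdrawal symptoms may appear within minutes of naloxone hydrochloride administration and subside in about 2 hours". Neither describes cortisol. If anything, both suggest an effect still present at 50 minutes rather than one that has gone.

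**The case for a change.** The best argument for a change is that it is cheap. Naming the time term takes a clause, needs no new samples and removes any suspicion of choosing the model after unblinding. Without a known time course, a test that does well in most shapes looks prudent: it wins in three of the four rows above, and at serial correlation .5 it gains about 20 points (.94 against .74) even when the effect is sustained.

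The arithmetic stands. So does the point that a recorded choice is better than an unrecorded one, and the analyst would do well to note it before the blind is broken after database lock (section 8.2). Three things keep this from being a defect.

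- The sentence does not commit to a slope. Categorical time is equally a linear mixed model, so the missed response depends on a model choice and a waning effect, neither of which the documents establish.
- The 2-df interaction test is not a test of rate and has no direction. Direction would come from two contrasts, each with a 95% CI half-width of about t(.975, 22) x sqrt(4/24) = .85 SD with independent errors. Making it the main test would demote the quantity that every statement of the objective and endpoint names.
- Further specification adds little. With order randomised 1:1, a visit effect averages out of the condition comparison if the two orders stay equal in number. Fitting period x time helps only if the change from baseline differs by visit. With an assumed 1 SD shift, half the effect left and independent errors, joint power rises from .42 to .51 (paired) or from .53 to .57 (random intercept). Detail can also do harm: a visit random intercept together with an unstructured within-visit covariance cannot be estimated, because the matrix already absorbs the intercept variance.

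**Conclusion.** The form of time is unstated, and a linear slope with separate baselines does come close to the 50-minute change from baseline. That is missing modelling detail on a secondary endpoint, which an analyst holding six samples per subject will have to settle and can settle sensibly, for instance by giving the changes at 20 and 50 minutes beside the slope.

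Choosing between a slope and a joint test is a trade-off. In the independent-error illustration it runs from 59 to 64 points in favour of the joint test, if a 1 SD effect vanishes by 50 minutes, to 11 to 13 points in favour of the slope when like error terms are compared, if the rise is linear. These sizes rest on an assumed effect, SD and correlation, and the documents do not say which shape is likelier. The slope answers the question as the plan words it. The primary nausea analysis and the 24 subjects are unaffected, and no change to the plan is called for.

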PLANNED INTERIM ANALYSES	Due to the current study design and safety profile of this test product, no interim analyses are planned.
STATISTICS Primary Analysis Plan	McNemar's tests will be performed to evaluate whether there is a statistically significant difference in nausea response (dichotomously scored as present or absent) across test product (intranasal naloxone) and control product (intranasal placebo) conditions.

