4 STUDY DESIGN

4.1 Study Overview

This is a single center, double-blind, placebo-controlled, randomized, crossover trial that will include 24 subjects. Subjects will be in the study for up to 3 weeks. Total time involved will be approximately 5-6 hours. There will be a period of at least 24 hours between study Visits 1 and 2.

4.2 Total Study Duration:

Total duration of subject participation will be up to 3 weeks, with one session of web-based screening, one session involving a telephone screening call to confirm eligibility and introduce the subject to the study and two lab sessions involving administration of test and control products (first lab session includes urine screen). Total duration of the study, including recruitment and subject study completion, is expected to be 6 months.

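### The 80%+ power claimed for N = 24 belongs to a one-tailed, one-sample binomial calculation, not to the McNemar test that will be run

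*Combined protocol and SAP*

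**What the plan says.** The design is a "crossover trial that will include 24 subjects" (section 4.1), and section 8.1 repeats the number: "Twenty-four eligible subjects will be randomly assigned". The primary analysis is McNemar's test. The synopsis describes it as evaluating a "difference in nausea response (dichotomously scored as present or absent) across test product (intranasal naloxone) and control product (intranasal placebo) conditions", and section 15.3 says that "tests will be performed to evaluate whether there is a statistically significant difference in nausea response". Neither place gives an alpha, a sidedness, a version (exact, mid-p, uncorrected or continuity-corrected) or an assumed rate of discordant pairs.

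The sample size rationale (synopsis and section 15.5) starts from "We do not expect any nausea responses to the control product". For each null p from .01 to .99 the authors "calculated the one-tailed rejection region" of a binomial, took its power at the alternative rate, and averaged over p with beta ordinates as weights. A bracketed remark concedes that "the entries in the table below do not correspond to standard power calculations for the McNemar test". The conclusion is nevertheless "For the values of potential interest to us, an N of 24 will suffice for 80%+ power".

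**The concern.** Power is a property of a particular test. McNemar's test uses only the discordant pairs, so its power depends on how often a subject has nausea on naloxone but not placebo, and the reverse. The plan's calculation has one sample, one proportion and a fixed null value. It treats the placebo rate as known up to a prior and never simulates or enumerates a pair.

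If the two calculations differ materially, the plan contains no valid statement of what 24 subjects can detect on the primary endpoint. A null result would then be read against a power that the test did not have. Because the version is also open, it could be chosen after the data are seen, and at this sample size the versions differ a great deal.

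**Working it through.** **1. Reproducing the plan's table.** Inputs from section 15.5: control and test rates, N per row, one-tailed region, grid p = .01 to .99. Assumed: alpha .05 and weights Beta(r, N − r) with r = N × control rate (r = 0 taken as 10⁻⁶). The second beta parameter is inferred from the match.

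For each p, let c(p) be the smallest c with P(Bin(N, p) ≥ c) ≤ .05. Then power = Σ w(p) · P(Bin(N, p_test) ≥ c(p)) / Σ w(p).

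| Control v test | N | Stated | Reproduced | Same method, N = 24 |
|---|---|---|---|---|
| 0 v 20% | 20 | .811 | .8112 | .876 |
| 0 v 30% | 12 | .823 | .8227 | .976 |
| 0 v 40% | 9 | .844 | .8437 | .996 |
| 10 v 40% | 16 | .817 | .8166 | .907 |
| 20 v 50% | 21 | .805 | .8049 | .843 |
| 30 v 60% | 24 | .805 | .8046 | .805 |

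All six rows match. Alpha .025 or .10 and the other beta parameterisations tried do not match all six. So the arithmetic is sound, and N = 24 does give at least 80% by this method.

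**2. McNemar with 0% control nausea.** Every discordant pair is then naloxone-only, so the number of discordant pairs is Bin(24, p_test). Each version rejects once that count reaches a threshold k, and power = P(Bin(24, p_test) ≥ k). No correlation assumption enters.

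| Version (alpha .05) | k, and why | 0 v 20% | 0 v 30% | 0 v 40% | Rate with 80% power |
|---|---|---|---|---|---|
| Exact two-sided | 6: 2 × .5⁶ = .031 (5 gives .0625) | .344 | .771 | .960 | 30.9% |
| Exact one-sided | 5: .5⁵ = .031 (4 gives .0625) | .540 | .889 | .987 | 26.4% |
| Mid-p two-sided | 5: .0625 − .031 = .031 | .540 | .889 | .987 | 26.4% |
| Uncorrected two-sided | 4: χ² = 4 > 3.84 | .736 | .958 | .996 | 21.8% |
| Uncorrected one-sided | 3: √3 = 1.73 > 1.645 | .885 | .988 | .999 | 17.0% |

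Continuity-corrected two-sided equals exact two-sided in these rows. Continuity-corrected one-sided equals exact one-sided, and mid-p one-sided equals uncorrected two-sided. Hence 0 v 20% misses 80% in seven of eight versions, 0 v 30% misses in two, and 0 v 40% in none.

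**3. McNemar with nonzero control nausea.** Let b be the naloxone-only count and c the placebo-only count. Power is the sum of trinomial probabilities of (b, c) over the rejection region, with P(naloxone-only) = p_test − p11 and P(placebo-only) = p_control − p11, where p11 is the probability of nausea on both. Under independence p11 = p_test × p_control.

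| Version, independence | 10 v 40% | 20 v 50% | 30 v 60% | Rows of six at 80% |
|---|---|---|---|---|
| Exact two-sided | .547 | .457 | .424 | 1 |
| Continuity-corrected two-sided | .547 | .453 | .415 | 1 |
| Exact one-sided, or continuity-corrected one-sided | .667 | .593 | .564 | 2 |
| Mid-p two-sided | .653 | .555 | .520 | 2 |
| Mid-p one-sided | .766 | .691 | .660 | 2 |
| Uncorrected two-sided | .656 | .555 | .520 | 2 |
| Uncorrected one-sided | .804 | .715 | .674 | 4 |

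**4. Sensitivity to within-subject correlation.**

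- *Maximal positive* (p11 = p_control, no placebo-only pairs): P(naloxone-only) is .30 in all three rows, so each equals 0 v 30% above. Exact two-sided gives .771 and still misses five of six rows. Exact one-sided and mid-p two-sided (.889) and uncorrected two-sided (.958) miss only 0 v 20%. Uncorrected one-sided (.988) misses none.
- *Halfway* (p11 midway between its independence and maximal values, i.e. .07, .15, .24): exact two-sided .641, .576, .547. Uncorrected one-sided .874, .827, .804, so that version reaches all six rows.
- *Most negative* (p11 = 0): exact two-sided .457, .347, .254.

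**The case against.** The strongest reply is that the plan discloses the mismatch: it tells the reader that the table is not standard McNemar power, and its arithmetic is correct for the method described. The failure in all six rows also needs independence between two responses of the same woman, which the plan does not assume. Already at the halfway correlation, uncorrected one-sided McNemar reaches 80% in every row, and one-tailed is the only sidedness the plan mentions. The rows with nonzero control rates were exploratory. In the 0% rows, 40% passes everywhere and 30% passes in six of eight versions. Finally, the study is partly a feasibility study.

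Some of this stands. The problem is a mismatch between sizing and analysis, not a slip in computation, and its size depends on choices that the plan leaves open. But the disclosure does not supply the missing figure: the plan still concludes that 24 subjects suffice, and gives no McNemar power anywhere. The bracketed gloss, which presents 0% v 40% as a test that both populations are at 20%, does not describe the one-sample calculation that reproduces the table. The version that rescues the claim is never named. It rejects at 3 v 0 discordant pairs, where the exact one-sided p-value is .5³ = .125. For 0 v 20%, no correlation helps any other version. The title claims efficacy as well as feasibility, and this is the only justification of N.

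**Conclusion.** The concern holds. The 80%+ statement is true of a beta-weighted, one-tailed, one-sample binomial method and is unsupported for the planned McNemar test. At N = 24, alpha .05 and independence, the eight versions reach 80% in between one row of six (exact and continuity-corrected two-sided) and four (uncorrected one-sided). In the plan's expected case of no control nausea, power for a 20% naloxone rate ranges from .344 to .885 by version, against .876 by the plan's method at the same N.

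Alpha .05 is an assumption, supported by the table's reproduction. Independence affects only the three rows with a nonzero control rate. Under positive correlation most versions improve there, but only uncorrected one-sided reaches all six rows. The statement must be corrected. The sample size and the choice of test can stay.

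**What to change.** In the synopsis and section 15.5, with the test definition carried into section 15.3:

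- Name the McNemar version, alpha and sidedness before any unblinded data are seen.
- Replace the table and the 80%+ sentence with McNemar power at N = 24 for that version. State the discordant-pair probabilities used: independence and at least one positive-correlation case for nonzero control rates.
- Add the naloxone nausea rate detectable with 80% power when control nausea is 0%: 30.9% (exact two-sided), 26.4% (exact one-sided or mid-p two-sided), 21.8% (uncorrected two-sided) or 17.0% (uncorrected one-sided).
- If the present table is kept, label it as one-sample binomial power and do not use it to support N.
- Editorial: drop the remark that a single nausea response would refute the null, since exact McNemar needs 6 v 0 discordant pairs two-sided or 5 v 0 one-sided. Drop also the description of the r = 0 prior as U-shaped: with the inferred parameters, about 98% of its weight at N = 20 lies at p ≤ .10.

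The cost is protocol and SAP wording only. No subjects are added and the test is unchanged. For most versions the stated power becomes less favourable.
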